The Florida Tobacco Quitline is operated by RVO Health, the largest provider of tobacco cessation quitlines in the U.S. RVO Health's Quit For Life® program is an evidence-based tobacco cessation treatment delivered over phone, web, and text, and is grounded in social cognitive theory and the U.S. Public Health Service clinical guidelines (PHS Guideline, 2008). Quitline coaches use cognitive behavioral therapy, reinforcement, and principles of self-efficacy to promote effective behavior change. The quitline approach includes 5 key elements: setting a quit date, coping with triggers, effectively using medications, tobacco proofing, and social support. Phone counseling for cessation has been evaluated in randomized trials and effectiveness studies (Hollis et al., 2007; Orleans et al., 1991; Stead et al., 2013; Zhu et al., 2002). Individuals who enroll in the quitline's multi-call program receive three phone calls. They are mailed two weeks of NRT after the first phone call, to begin using on their quit date (coinciding with the second call). Participants will be provided with information about the study during their first phone call, and study staff will reach out to enroll participants in the study after receiving their contact information from the Quitline.

Study Arms

Quitline Only (QLO). Participants randomized to the QLO condition will receive an app that administers the daily diary questions for 5 weeks and shows their app and abstinence related progress. They will not receive any treatment via the app. Thus, they will receive usual care via the quitline and complete minimal daily assessments.

Quitline plus AR (QL+AR). Participants randomized to QL+AR will receive the AR app described in Aim 1. Initially, the app will only administer the daily diary questions. Once 48 hours of self-reported tobacco abstinence is achieved, the AR elements of the app will become available (see 4.2). Daily diary questions will continue for 5 weeks. AR extinction trials will occur daily until (1) the participant reports 3 consecutive days of smoking, in which case the AR trials will be suspended until another smoke-free 48 hours are reported, or (2) a

total of 5 weeks have elapsed since the start of app use.

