Follow-up questionnaires will be sent to all participants via REDCap around 5 weeks and 6 months after-baseline completion. A subset of participants (40%, approximately 100) who self-report cigarette smoking abstinence at around 6 months will be mailed a saliva collection kit for cotinine-based biochemical confirmation of abstinence. A subset of participants (n=40) from QL+AR will complete a phone interview at the end of treatment, as will a subset of quitline supervisors (n=10) and all App coaches.

Compensation and Retention

For completion of measures at baseline, and around 5 weeks and 6 months after baseline survey completion, participants will receive a \$20 gift card (up to \$60 total). For each week they complete at least 70% of the daily diary questions (5 days), they will receive a \$10 gift card (up to \$50 total). Thus, most participants will be compensated up to \$110. Participants who complete the interview, will be compensated \$20. Participants who return a saliva sample will be compensated \$25.

To aid in retention, the following procedures will take place: collection of full contact information; text reminders and phone calls to follow-up on incomplete surveys; and collection of names and contact information of at least 2 collaterals (i.e., relatives, friends) who can help us reach lost participants.

Treatment Delivery and Fidelity for AR and Quitline Coaching

Although we expect minimal use of App coaches based on the comprehensive app content, we will monitor and assess coaching fidelity. App coaches will be part of the study team. With an eye toward scalability, qualifications will mimic those of quitline coaches (e.g., Bachelor's degree, tobacco abstinent). Training will be manualized and conducted by Drs. [name] and [name], given their experience with exposure-based treatments. Training (8-10 hours) will be a combination of reading, didactics, and role playing. We will develop a measure to assess adherence and competence to be used during the training period. Weekly supervision will occur to ensure App coaching is delivered consistently. Coaches falling below performance

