4.4 Measures

AIM 1 Measures

Baseline Measures. Participants will complete a series of baseline measures, administered via REDCap link, to assess demographics, experience with AR, and smoking history.

Daily Diary Questions. Each morning, participants will report via the app: number of cigarettes smoked from previous day; previous day's use of NRT, e-cigarettes, and other tobacco products; and current urge to smoke, assessed on a 10-point Likert scale (see appendices).

Urge and Situation during AR Sessions. Participants will rate their urge (craving) to smoke on a single 10-point Likert scale. Single-item scales reduce participant burden when multiple ratings are required, and they have been found to be reliable and valid in assessing urge to smoke (Kozlowski et al., 1996). The circumstances surrounding app use (e.g., at home, alone, with alcohol, etc.) will be assessed.

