indicator of treatment engagement. Primary treatment engagement variables of interest that are linked to our theoretical model of extinction and that are related to increased abstinence include: greater completion of the AR sessions (e.g., multiple times per day over several days), conducting the AR sessions in several different locations (to increase generalizability of extinction), and less use of avoidance strategies during the AR sessions (e.g., using distraction or other behaviors to avoid experiencing craving). Avoidance strategies will be assessed at the 5 week survey via a checklist of avoidance strategies and the frequency that they occurred during AR sessions. We will also collect self-reported treatment satisfaction using a modified version of the Client Satisfaction Questionnaire (Attkisson & Greenfield, 1994), the SUS (Brooke et al., 1996; Lewis & Sauro, 2009), and unique items to assess features and functions of the app and the AR experience, including the App coach. Extinction magnitude (degree of craving reduction over time) and latency (time to meeting extinction criteria) will also be derived. For participants who never achieved abstinence during the 5 weeks of app use, thus, never completed AR sessions, versions of the follow-up surveys will omit items specifically related to AR use. For participants who achieved abstinence, but did not complete more than 4 AR sessions, there will be questions at the 5-week survey regarding barriers to completing the AR sessions.

Quitline Usage and App Coaching. Basic information on participant interactions will be provided to the study team from the quitline, including call completion dates, quit status (planned and actual quit dates), and NRT that was shipped. For those in QL+AR, we will track calls completed with an App coach.

Tobacco Abstinence. The primary outcome measure will be 7-day point prevalence abstinence (defined as self-report of no combustible tobacco use in the past 7 days; Piper et al., 2020) around 6 months post-baseline. Reported abstinence will be confirmed in approximately 40% of self-reported abstinent participants using a saliva cotinine level cut-off of <10 ng/ml (Benowitz et al., 2020). Cotinine analysis using ELISA assay will be conducted by Salimetrics (Carlsbad, CA).

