Aim 2a. The primary test of the efficacy of QL+AR over QLO will use logistic regression on biochemically-confirmed abstinence around 6 months after baseline survey completion. This will be performed on the 20 imputed data sets using those participants who exhibited 48 hours of abstinence (n=1450). The model will include demographics and smoking-related variables that were found to uniquely predict self-reported abstinence at 6 months based on preliminary analyses. A parallel analysis will be performed to evaluate efficacy for all enrolled (N=2072; i.e., beyond those who exhibit the required 48-hour abstinence to engage the AR intervention). A second test of effectiveness will use generalized estimating equations (GEE) with both the 5-week and 6-month abstinence as the outcomes. This approach permits evaluation of a change in abstinence from around 5 weeks to 6 months and an assessment of the intervention at around 5 weeks in the context of the primary outcome (using a timespecific contrast).

Aim 2b. Prospective moderators of the QL+AR intervention will be explored, separately, by extending the analyses described above through the inclusion of the moderator and the moderator x intervention as predictors of the dependent measure. A significant interaction term supports the variable as a moderator, which will be explored by assessing condition differences for each level of categorical moderators and for levels of continuous moderators created via median splits, tertiles, or quartiles. The following baseline measures will be evaluated: sex, nicotine dependence, trait cue reactivity, smoking status during treatment, quitline use, and NRT use.

Prospective predictors of the AR intervention will be evaluated using only participants from the QL+AR arm. Similar to the analyses described above, AR-related variables will be added to a logistic regression model of abstinence at around 6 months that includes demographics and baseline smoking-related variables found to be predictors of abstinence among QL+AR participants. The following variables will be explored: initial cue reactivity, extinction magnitude and latency, indices of treatment engagement, and App coach use.

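### Six-month abstinence excludes only combustible tobacco but is confirmed by cotinine, and the plan does not say how abstainers using NRT or e-cigarettes are scored

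*Combined protocol and SAP*

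**What the plan says.** All references are to the combined protocol and SAP.

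- **Definition (4.4 Measures, Tobacco Abstinence).** The primary outcome is 7-day point prevalence abstinence at about 6 months, "defined as self-report of no combustible tobacco use in the past 7 days". Nicotine from NRT or e-cigarettes does not count against a participant.
- **Confirmation (same paragraph).** Reports are confirmed in roughly 40% of self-reported abstainers "using a saliva cotinine level cut-off of <10 ng/ml". The only test named is cotinine: "Cotinine analysis using ELISA assay will be conducted by Salimetrics".
- **Who is tested (4.3, End of Treatment and Follow-up).** "A subset of participants (40%, approximately 100) who self-report cigarette smoking abstinence at around 6 months" are mailed a saliva kit.
- **Primary analysis (section 5, Aim 2a).** The efficacy test "will use logistic regression on biochemically-confirmed abstinence around 6 months after baseline survey completion", on 20 imputed data sets.
- **Nicotine products in the trial.** The quitline supplies NRT in both arms: "They are mailed two weeks of NRT after the first phone call, to begin using on their quit date" (4.3, Quitline Services). The app diary asks about "previous day's use of NRT, e-cigarettes, and other tobacco products" (4.4), but it runs for only 5 weeks. The Aim 2 eligibility criteria (3.2) do not exclude e-cigarette users.

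**The concern.** The definition and the test measure different things. The definition permits non-combustible nicotine. The test detects nicotine exposure whatever its source, because cotinine is its metabolite. Someone who has stopped smoking but was vaping, or using gum or a patch, shortly before the 6-month sample satisfies the definition and can still exceed the cut-off.

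The plan does not resolve the conflict. It names no marker that separates smoking from other nicotine use, does not exempt declared users, and does not say how a positive result is coded. It also does not say how the untested 60% or so of abstainers enter a confirmed endpoint.

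Three things are at stake. The reported abstinence rates could be too low. Power could fall. If use of these products at 6 months differs between arms, the treatment estimate could be biased. The incremental cost per quitter in Aim 3a uses the same endpoint and would inherit any error.

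**Working it through.** **Inputs from section 5, Sample Size and Study Power Analysis.** 725 per arm, 10% in QLO against 15% in QL+AR, two-sided alpha .05, 5% of variance taken by covariates. From 4.3 and 4.4: 40% of self-reported abstainers tested.

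**Step 1: reproduce the plan's power.** Effective n = 725 × .95 = 688.75 per arm. The formula for two proportions with pooled variance under the null is

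power = Φ{[|p2 − p1|√n − 1.96√(2p̄(1 − p̄))] / √(p1(1 − p1) + p2(1 − p2))}

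With p1 = .10, p2 = .15 and p̄ = .125 this is Φ{(1.312 − .917)/.466} = .80. The odds ratio is (.15/.85)/(.10/.90) = 1.59. Both agree with the plan.

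**Step 2: number of kits.** Expected abstainers are 725 × (.10 + .15) ≈ 181, and 40% of these is about 73. The plan says about 100, which would imply 100/.40 = 250 abstainers. If a share f of tested abstainers use nicotine products and all of them fail, then f = 10% to 30% gives about 7 to 22 failures among 73 kits, or 10 to 30 among 100, that are not due to smoking.

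**Step 3: effect on the endpoint.** The documents give no value for f, so 10% to 30% is an assumption. Multiply each arm's rate by (1 − f × c), where c is the share of abstainers who can fail:

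- c = .40: only tested abstainers can fail, and untested self-reports are accepted.
- c = 1: failures carry over to all abstainers. This could happen if untested cases were treated as missing and imputed from tested ones. The plan does not say that they are.

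Equal use in both arms:

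| f | c = .40: rates | OR | power | c = 1: rates | OR | power |
|---|---|---|---|---|---|---|
| 10% | 9.6% / 14.4% | 1.58 | .78 | 9.0% / 13.5% | 1.58 | .75 |
| 20% | 9.2% / 13.8% | 1.58 | .76 | 8.0% / 12.0% | 1.57 | .70 |
| 30% | 8.8% / 13.2% | 1.58 | .74 | 7.0% / 10.5% | 1.56 | .63 |

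Unequal use, same formulas:

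| f in QLO / QL+AR | c = .40: rates | OR | power | c = 1: rates | OR | power |
|---|---|---|---|---|---|---|
| 10% / 20% | 9.6% / 13.8% | 1.51 | .68 | 9.0% / 12.0% | 1.38 | .44 |
| 20% / 10% | 9.2% / 14.4% | 1.66 | .85 | 8.0% / 13.5% | 1.79 | .91 |

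For example, (.138/.862)/(.096/.904) = 1.51 and (.135/.865)/(.08/.92) = 1.79. The higher power in the last row reflects an inflated odds ratio and is not a gain.

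**The case against.** A reader might draw four stronger conclusions, and the documents support none of them.

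- **That nicotine-using abstainers will be counted as smokers.** The plan never says how a positive result is coded. Section 4.4 presents the outcome as self-report with a sample confirmed, so the saliva test could be meant only as a check on self-report, with no individual recoded. Against that, 4.4 and section 5 name confirmed abstinence as what is analysed. The supportable statement is that such people can fail and that their scoring is unspecified.
- **That quitline NRT causes the problem.** The supply is two weeks from the quit date, so it should rarely matter at 6 months. E-cigarettes and self-obtained NRT are the likelier sources. The 5-week diary bears on early use only.
- **That the comparison is biased against QL+AR.** No passage shows different use by arm at 6 months. The app's guidance on nicotine products before AR sessions (4.2) goes to one arm only, but app treatment ends at about 5 weeks. Bias could run in either direction.
- **That the 6-month survey omits nicotine products.** The measures described for follow-up do not name such an item. However, the list is partly illustrative, and the survey appendix provided is for Aim 1. The item may exist, but even so no rule says how to use it.

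It is also fair to object that the c = 1 figures overstate the loss if untested reports are simply accepted. That stands, which is why both cases are shown.

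**Conclusion.** The mismatch is real: within one paragraph of 4.4 the definition permits non-combustible nicotine and the confirmatory test does not, and nothing elsewhere reconciles them. Its size is modest to moderate and cannot be fixed from the documents. Under an assumed 10% to 30% use in both arms, power is .78 to .74 if only the tested 40% can fail, and .75 to .63 if failures carry over to everyone. Equal use leaves the odds ratio at 1.56 to 1.58 against 1.59, so the cost is in rates and power. A 10-point difference in use between arms moves it to 1.51 or 1.66 (40% tested), or 1.38 or 1.79 (all), depending on which arm uses more.

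These figures assume that every nicotine user fails the cut-off and is scored as not abstinent. The plan's power figure is correct on its own inputs; it simply contains no allowance for this loss. The point should be addressed, but it does not undermine the design.

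**What to change.** 1. Make sure that the 6-month survey and the form returned with the saliva kit ask about past-7-day use of NRT, e-cigarettes and other non-combustible nicotine. Without this, a positive result cannot be attributed to smoking or to permitted use.
2. State in section 5 that a cotinine result at or above the cut-off reclassifies only participants who report no such use.
3. In the main analysis, let declared users keep their self-reported combustible status. Add a sensitivity analysis that counts them as not abstinent.
4. State how untested abstainers enter the confirmed endpoint, because this decides which column of the tables applies.

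The cost is at most one survey item, one line on the kit form and a few sentences in the plan, with no extra assay. The downside is that declared nicotine users are not biochemically verified. About 60% of abstainers are already in that position, and the sensitivity analysis bounds the effect. Aligning the definition with the assay, or adding a marker specific to smoking, would also remove the conflict, but the first changes the endpoint and the second adds laboratory work.

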4.5 Adverse Reactions

Minimal risks are anticipated for this study and are described below. Risk mitigation strategies are described in the Adequacy of Protection Against Risks. This study involves no investigational drugs or devices.

- Data including self-report, interview (psychological and medical), and/or biological samples (e.g., saliva) involve risk of breaches in confidentiality. Participants will always be given the option to refuse to answer any questions on the measures that may be distressing. This is the only risk that also applies to quitline supervisors.
- For data collected via smartphone, there are always risks associated with privacy when collecting data in this format.
- There may also be an increased risk of using cigarettes due to increased craving experienced during some of the AR sessions.
- Successful abstinence may cause irritability, anxiety, general distress, and difficulty concentrating.
- Nicotine replacement therapy (NRT) will be provided via the quitline per their usual treatment procedures and will be the appropriate dose based on level of smoking and should aid in the management of withdrawal symptoms. NRT and smoking cessation counseling have been shown to be safe and effective for smokers attempting to quit (e.g., NRT is available over-the-counter). However, side effects of NRT may occur and include skin irritation/ rash (for the patch), nausea, dizziness, dry mouth, diarrhea, nervousness, headache, vivid dreams or sleep disturbances, irritability, and irregular heartbeat.

5. STATISTICAL CONSIDERATIONS

Data Management and Statistical Considerations for Aim 1

Compliance will be calculated for the completion of AR urge and daily diary questions. We will also observe the use of various features to determine general use/engagement. The SUS will be scored according to scale instructions, with an expected mean above 68. Interview responses will be reviewed for common themes. Modifications to the app will be made based on these findings. In the unlikely event that major changes need to be made based on participant feedback, we will repeat the procedures for this aim to gather additional feedback on the revised app. Any major changes will be field tested in a similar manner prior to the onset of the RCT in Aim 2.

Data Management and Statistical Considerations for Aims 2 and 3

Overview of Data Management and Statistical Considerations for Aim 2

Based on abstinence rates from quitline/telephone counseling (Fiore et al., 2008; Matkin et al., 2019; Pinerio et al., 2020), the estimated abstinence rate around 6 months for the QLO condition is 10%. With 1036 randomized to each condition, power was calculated for the 725 participants expected to achieve 48-hours of abstinence in each condition (to activate the AR app). Power $\geq .80$ to detect an abstinence rate of at least 15% (OR = 1.59) in the QL+AR condition using alpha = .05, a 2-sided test, and allowing 5% of variance in abstinence rates to be accounted for by other variables. Treatment group differences in baseline measures will be assessed and any variable with a group difference of $p < .10$ will be incorporated into analyses focusing on

intervention effects. To manage missing data, multiple imputation under the Missing at Random assumption will be applied using a Markov Chain Monte Carlo method. The primary statistical analysis for Aim 2 will use logistic regression to compare biochemically-confirmed abstinence rates at the 6-month assessment between conditions. A parallel analysis will be performed to evaluate efficacy for all enrolled (N=2072; i.e., beyond those who exhibit the required 48-hour abstinence to engage the AR intervention). A second test of effectiveness will use generalized estimating equations (GEE) with both the 5-week and 6-month abstinence as the outcomes. Please see the Statistical Design and Power attachment for additional details on our statistical approach.

Data Management. Baseline, 5-week, and 6-month survey data will be exported from REDCap as .CSV files, which will be read into SAS version 9.4 (SAS Institute, Cary, NC) on a weekly basis during data collection. Data review and primary data analyses will be performed using SAS version 9.4. [name] will oversee the data management, provide the PIs with reports and summaries on a regular basis, and perform the final analyses.

Sample Size and Study Power Analysis. The primary statistical analysis for Aim 2 will use logistic regression to compare abstinence rates at the 6-month assessment between QL+AR and QLO conditions. Preliminary analyses will be used to identify demographics and tobacco history variables that predict either missing surveys or abstinence around 5 weeks and 6 months. These variables will be used in a multiple imputation model to manage missing data. Based on abstinence rates from quitline/telephone counseling (Fiore et al., 2008; Matkin et al., 2019; Pinero et al., 2020), the estimated 7-day point prevalence abstinence rate around 6 months for the QLO condition is 10%. With 1036 randomized to each condition, power was calculated for the 725 participants expected to achieve 48-hours of abstinence in each condition (to activate the AR app). Power $\geq .80$ to detect an abstinence rate of at least 15% (OR = 1.59) in the QL+AR condition using alpha = .05, a 2-sided test, and allowing 5% of variance in abstinence rates to be accounted for by other variables. A comparable analysis using all 2072 randomized participants (the 1450 who do achieve 48-hours of abstinence plus the 622 who do not) will have lower expected abstinence rates. Estimating that 7% of all QLO participants will be abstinent, power $> .80$ to detect an abstinence rate of at least 10.6% for QL+AR (OR = 1.57) using alpha = .05, a 2-sided test, and allowing 5% of variance in abstinence rates to be accounted for by other variables.

Data Analysis Overview. Descriptive statistics will be used to review all variables in the study prior to hypothesis testing. Data transformations will be made as needed. Treatment group differences in baseline measures will be assessed and any variable with a group difference of $p < .10$ will be incorporated into analyses focusing on intervention effects. All analyses described below will be performed for those who achieved 48 hours of self-reported abstinence (n=1450) as well as the full sample of those enrolled (N=3590). The former is relevant to assessing the efficacy of the app specifically, whereas the latter will reflect the overall incremental effectiveness of the app from the perspective of the quitline. Full-sample versus AR-sample differences in baseline measures will be evaluated.

To manage missing data, multiple imputation under the Missing at Random assumption will be applied using a Markov Chain Monte Carlo method (Schafer, 1997) via PROC MI in SAS, given the expected nonmonotonic missing data patterns and the expected large number of auxiliary variables (e.g., baseline measures that predict smoking status at follow-up) to be determined by preliminary analyses. The imputation model will

include smoking status around 5 weeks, which is expected to be a primary predictor of smoking status around 6 months.

In addition, any other measures acquired around 5 weeks that are unique predictors of missingness or smoking status around 6 months will be included in the imputation model. Finally, a post hoc approach (Rubin, 1987) will address the possible influence of Missing Not at Random. As done in recent studies (e.g., [name] et al., 2016; Martinez et al., in press), the post hoc adjustment will be small-to-medium in size (akin to Cohen's $d=0.35$) in accordance with missing implies smoking. Twenty data sets will be generated. Therefore, all analyses of the primary outcome will be performed on complete data sets (i.e., intent-to-treat) following multiple imputation.

Analytic Plan for Addressing Specific Aims.

Aim 2a. The primary test of the efficacy of QL+AR over QLO will use logistic regression on biochemically-confirmed abstinence around 6 months after baseline survey completion. This will be performed on the 20 imputed data sets using those participants who exhibited 48 hours of abstinence (n=1450). The model will include demographics and smoking-related variables that were found to uniquely predict self-reported abstinence at 6 months based on preliminary analyses. A parallel analysis will be performed to evaluate efficacy for all enrolled (N=2072; i.e., beyond those who exhibit the required 48-hour abstinence to engage the AR intervention). A second test of effectiveness will use generalized estimating equations (GEE) with both the 5-week and 6-month abstinence as the outcomes. This approach permits evaluation of a change in abstinence from around 5 weeks to 6 months and an assessment of the intervention at around 5 weeks in the context of the primary outcome (using a timespecific contrast).

Aim 2b. Prospective moderators of the QL+AR intervention will be explored, separately, by extending the analyses described above through the inclusion of the moderator and the moderator x intervention as predictors of the dependent measure. A significant interaction term supports the variable as a moderator, which will be explored by assessing condition differences for each level of categorical moderators and for levels of continuous moderators created via median splits, tertiles, or quartiles. The following baseline measures will be evaluated: sex, nicotine dependence, trait cue reactivity, smoking status during treatment, quitline use, and NRT use.

Prospective predictors of the AR intervention will be evaluated using only participants from the QL+AR arm. Similar to the analyses described above, AR-related variables will be added to a logistic regression model of abstinence at around 6 months that includes demographics and baseline smoking-related variables found to be predictors of abstinence among QL+AR participants. The following variables will be explored: initial cue reactivity, extinction magnitude and latency, indices of treatment engagement, and App coach use.

Aim 3a. Our preliminary cost-effectiveness assessment will use the primary trial endpoint of smoking abstinence at around 6 months as the main effectiveness/outcome measure. Using this outcome, we will calculate the incremental cost-effectiveness of the QL+AR arm compared to the QLO arm in increasing smoking abstinence

(e.g., cost per quitter). Finally, we will also use quality adjusted life years (QALYs) and lifetime medical costs to estimate more inclusive, life-long effect and cost-effectiveness of the intervention. We will use the most recent estimates in the literature (e.g., Feirman et al., 2016; Kaplan et al., 2007) to estimate QALYs and lifetime medical costs associated with smokers and smoking cessation. We will assess the robustness of incremental results between the two study arms using probabilistic sensitivity analysis. Cost-assessments and cost effectiveness will be calculated on the basis of both all enrolled participants as well as only those who qualified for the AR intervention by achieving 48 hours of abstinence.

Aims 3b and 3c. Descriptive statistics will be used to evaluate treatment engagement (measured via greater completion of the AR sessions, conducting the AR sessions in several different locations, and less use of avoidance strategies during the AR sessions), acceptability (measured via the Client Satisfaction Questionnaire, System Usability Scale, and unique items that assess app features, functions, and the AR experience including the App coach). Variables derived from engagement with the app will be explored as predictors in multivariable models that already include baseline predictors.

Qualitative methods will be used to identify facilitators and barriers to app usage. We will use thematic analysis to analyze the key stakeholder interviews (quitline supervisors, App coaches, subset of participants; Creswell, 2007). We will develop a list of a priori codes based on the domains identified in the interview guide to develop an initial codebook. Two trained qualitative analysts from Moffitt's Participant Research Interventions and Measurement Core will independently code an initial set of transcripts (n=5). After the first round of coding is complete, they will discuss their notes on possible new codes (e.g., themes that emerge from the data) and refine the codebook. The analysts will code another initial set of transcripts (n=5) and

